2.5.2 Physical examination

Subjects with any abnormal physical examination findings at screening will be listed (Listing 2). Changes in physical examination findings from screening to end of trial will be recorded as AEs if they are untoward or the investigator judges them to be clinically significant changes.

2.5.3 Vital signs

BP and heart rate immediately before and after administration of G-Pen™ in each age group and by treatment dose for subjects aged 12.0-<18.0 will be summarized by descriptive statistics (Table 14 and Figure 4).

2.5.4 Local Tolerability

The incidence of any injection site discomfort (i.e., FPS-R score >0 on the ordinal rating scale) by age group and by treatment dose for subjects aged 12.0-<18.0 will be analyzed descriptively (Table 15 and Figure 5). The incidences of erythema (Table 16 and Figure 5) and edema (Table 17, and Figure 5) will be analyzed in a similar manner. Descriptive statistics will be provided for time of onset, duration (of discomfort), and discomfort description (i.e., pain, irritation, itching, etc.) by age group and by treatment dose for subjects aged 12.0-<18.0 (Table 18).

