9. After 5 minutes, a confirmatory plasma glucose measurement will be performed.
  - a. If plasma glucose remains  $< 80$  mg/dL, collect a second baseline PK blood sample, and begin administration of the study drug (see Section 9.3.2).
  - b. If plasma glucose has risen to  $\geq 80$  mg/dL, return to step 7b and repeat the process.
10. Following study dosing, plasma glucose will be measured every  $5 \pm 2$  minutes until 90 minutes post-dosing.

11. Additional blood samples will be collected at 10, 20, 30, 45, 60, 90, 120, and 180 minutes post-dosing, with  $\pm 5$  minutes per collection, and processed and stored at  $-80 \pm 20$  C for determination of plasma glucagon levels.
12. After completing all collections and procedures at 180 minutes post-dosing, the subject will be given a meal as per the standard practice at each site, and their usual dose of insulin. The subject can then leave the clinic after plasma glucose is confirmed to be between 70 and 180 mg/dL.
13. Local tolerability will be assessed as follows:
  - a. Subjects will complete age-appropriate questionnaires regarding injection site discomfort ([Appendix 1](#)) at  $10 \pm 5$  and  $30 \pm 5$  minutes post-dosing, and again at  $180 \pm 5$  minutes post-dosing if the FPS score reported at 30 minutes is  $> 0$ .
  - b. An investigator will use the modified Draize scales ([Appendix 2](#)) to assess erythema and edema formation at the injection site at  $10 \pm 5$  and  $30 \pm 5$  minutes following administration. Any injection site with a score  $> 0$  for either erythema or edema at 30 minutes post-dosing will be re-evaluated for both at  $180 \pm 5$  minutes post-dosing.
14. Adverse events reported by the subject or observed by an investigator will be recorded in Advantage eClinical and managed as medically appropriate.

If a subject exhibits signs of distress at any time post-dosing or if plasma glucose drops below  $< 70$  mg/dL, glucose tablets may be given at the discretion of the investigator. Signs and symptoms should be monitored and if the subject's condition fails to improve within 15 minutes, additional glucose tablets or other intervention (e.g., IV dextrose) may be given at the discretion of the investigator. Every attempt should be made to complete all remaining safety and efficacy evaluations, to the extent this can be done while safeguarding the subject.

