### 12.2. Reporting Adverse Events

All observed or volunteered AEs regardless of treatment group or suspected causal relationship to the study treatment will be reported with the exception that injection site reactions will not be considered an AE unless a skin reaction or pain requires medical intervention.

For all AEs, the investigator must pursue and attempt to obtain information adequate to determine the outcome of the AE and to assess whether it meets the FDA criteria for classification as an SAE, requiring immediate entry of applicable information into Advantage eClinical. For AEs with a causal relationship to the investigational product, follow-up by the investigator is required until the event resolves or stabilizes at a level acceptable to the investigator to consider it closed, and the Medical Monitor should concur with that assessment.

As part of ongoing safety reviews conducted by the Sponsor, any non-serious adverse event that is determined to be serious (according to the FDA definitions of an SAE) will be reported by the Sponsor as a SAE. To assist in the determination of case seriousness, further information may be requested from the investigator to provide clarity and understanding of the event in the context of the clinical study.

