### **13.3.4. Local Tolerability:**

The incidence of any injection site discomfort (score >0 on the ordinal rating scale) will be analyzed descriptively. The incidences of erythema and edema will be analyzed in a similar manner. Descriptive statistics (only) will be provided for time of onset and duration (of discomfort) and discomfort description (i.e., pain, irritation, itching, etc.).

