### Faces Pain Scale – Revised (FPS-R)

*Investigative Site Instructions:* The subject should complete the FPS-R regarding injection site discomfort at both **10±5** minutes and **30±5** minutes following the injection of study drug, and again before the end of the clinic visit if the FPS score at **30±5** minutes is > 0. The subject completes the FPS by choosing the face that corresponds to their current level of pain. The goal is for the subject to report the amount of discomfort, if any, remaining at each time point, as opposed to reporting the transient pain associated with needle insertion.

Show the faces to the subject and provide the following instructions, using the words “hurt” or “pain,” whichever seems right for a particular subject:

**“These faces show how much something can hurt. This face [point to the face on far left] shows no pain. The faces show more and more pain [point to each from left to right] up to this one [point to face on far right] – It shows very much pain. Point to the face that shows how much you hurt right now.”**

Score the chosen face 0, 2, 4, 6, 8 or 10, counting left to right, so 0 = no pain and 10 = very much pain.

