## APPENDIX 2. DRAIZE SCALE

*Study Personnel Instructions:* The modified Draize Scale as shown in the table below will be used for physical examination/rating of abnormalities at the injection site.

The injection site should be examined for formation of both erythema and edema and results recorded in the Case Report Form. Evaluations of the injection site should be performed at 10±5 and 30±5 minutes post-treatment, and again at the end of the treatment visit (i.e., at approximately 180±5 minutes post-dosing) if any scores > 0 were noted at 30-minutes post-dosing.

Erythema Formation		Edema Formation	
Description	Score	Description	Score
No erythema	0	No edema	0
Very slight erythema Barely perceptible	1	Very slight edema Barely perceptible	1
Well defined erythema	2	Well defined edema	2
Moderate erythema	3	Moderate edema Raised approx. 1 mm	3
Severe erythema Beet redness to slight eschar formation	4	Severe edema Raised more than 1 mm and beyond exposure area	4

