1.2.2 Secondary Endpoints

The secondary endpoints for this study are as follows:

- PK parameters, including: descriptive analysis of serum glucagon AUC_{0-180m} , C_{max} and T_{max} of the different age group and overall population. These analyses will be conducted by IMD (See Appendix II).
- PD characteristics, including: descriptive analysis of plasma glucose AUC_{0-90m} , C_{max} , T_{max} and time to achieve an increase in plasma glucose of at least 25 mg/dL for each age group. In addition, in the 12.0-<18.0 year-old age group, plasma glucose change from baseline to 30 minutes after administration of G-Pen™ at a dose of 0.5 mg will be evaluated.
- Safety-related endpoints including:
 - Vital signs, including blood pressure (BP) and heart rate.
 - Incidence of adverse events (AEs) and serious adverse events (SAEs).
 - Subjective injection site discomfort assessed using the Faces Pain Scale (FPS-R).
 - Subjects with sufficient comprehension will further describe the nature and duration of any injection site discomfort using a second questionnaire.
 - Erythema and/or edema formation at site of injection assessed by an investigator using the modified Draize Scale.

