2 ANALYSIS PLAN

All endpoints will be analyzed descriptively within each of the three age groups. N (non-missing sample size), mean, standard deviation, median, minimum, and maximum will be presented for continuous variables. Count and percentage (based on the non-missing sample size) will be presented for discrete variables.

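### Injection-site pain, erythema and edema are summarised only as score above 0, so no visible table or listing shows the intensity of reactions that needed no medical intervention, and the 180-minute denominator is left open.

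*SAP*

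**What the plan says.** **What is collected.** For FPS-R, Protocol Appendix 1 instructs staff: "Score the chosen face 0, 2, 4, 6, 8 or 10". That gives six levels. Protocol Appendix 2 grades erythema and edema separately from 0 to 4. Erythema grade 1 is barely perceptible and grade 4 is described as "Beet redness to slight eschar formation". Both scales are named secondary safety endpoints. For the second, SAP 1.2.2 has: "Erythema and/or edema formation at site of injection assessed by an investigator using the modified Draize Scale".

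**What is summarised.** SAP 2.5.4 specifies "The incidence of any injection site discomfort (i.e., FPS-R score >0 on the ordinal rating scale", by age group and by dose in adolescents. Protocol 13.3.4 uses the same cut at 0 for discomfort and adds: "The incidences of erythema and edema will be analyzed in a similar manner". In SAP Appendix I the discomfort, erythema and edema shells (captioned Tables 16 to 18, cited in 2.5.4 as Tables 15 to 17) give n and % at 10, 30 and 180 minutes. Their footnotes define the event as a score above 0.

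**What goes to the adverse event tables.** Protocol 12.2 states that "injection site reactions will not be considered an AE unless a skin reaction or pain requires medical intervention".

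**When the 180-minute score is taken.** Under Protocol 10.2.1, step 13, FPS-R is repeated at 180 minutes only if the 30-minute score was above 0. For Draize, a site scoring above 0 "for either erythema or edema at 30 minutes post-dosing will be re-evaluated for both". SAP 2 sets the general rule for percentages: "Count and percentage (based on the non-missing sample size) will be presented for discrete variables".

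**The concern.** Tolerability in each age group is a secondary objective, and the product is a DMSO-based injection given to children from age 2. Graded data are recorded and then cut at 0. A reader learns how many children reacted at each time and, for discomfort only, its onset, duration and type. The reader does not learn whether the reactions were faint or strong, whether strength differed by age group, or whether 1 mg was worse than 0.5 mg in adolescents who received both.

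The gap matters most for the youngest group. The duration and description shell carries a footnote for children too young to answer that questionnaire. For them FPS-R is the only self-report, and it is shown as yes or no.

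The 180-minute column of the same shells raises a second question. If only children who still had a reaction at 30 minutes are scored again, and percentages use non-missing scores, children without a reaction drop out of the denominator.

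**Working it through.** There is no figure in the plan to reproduce. The check compares what is collected with what each visible output can show, then works through the denominator.

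**1. Levels lost at the cut.** FPS-R has levels 0, 2, 4, 6, 8 and 10, so an entry above 0 merges 6 − 1 = 5 of 6 levels. Draize has levels 0 to 4, so it merges 5 − 1 = 4 of 5, for erythema and for edema.

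Take 6 children, 3 of whom react (assumed counts). If all three score FPS-R 2, the shell prints n = 3 and 3/6 = 50%. If all three score 10, it prints the same. The median and maximum over the 6 children would be (0 + 2)/2 = 1 and 2 in the first case, and (0 + 10)/2 = 5 and 10 in the second.

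**2. Whether another visible output fills the gap.**
- The adverse event severity tables take injection-site reactions only if intervention was needed (Protocol 12.2).
- The shell captioned Table 19 gives onset, duration and type of discomfort. It has no intensity and does not cover erythema or edema.
- Listings 1 to 3 cover protocol deviations, abnormal screening examinations and pregnancies.
- Figure 5 is not visible. SAP 2.5.4 cites it alongside the incidence tables and for nothing else.

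**3. The 180-minute percentage.** Assume 6 children dosed, m of them re-scored, and 1 still above 0.
- All dosed as denominator: 1/6 = 16.7%.
- Non-missing scores as denominator: 1/m, which is higher by the factor 6/m.

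| m re-scored | 1/m | factor 6/m |
|---|---|---|
| 1 | 100% | 6 |
| 2 | 50% | 3 |
| 3 | 33.3% | 2 |
| 4 | 25% | 1.5 |
| 5 | 20% | 1.2 |
| 6 | 16.7% | 1 |

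The count n is 1 in every row. Only the percentage moves.

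**4. Size of the additions.**
- Present count cells: 3 tables × 4 age/dose groups × 3 times = 36.
- Median and maximum of the worst score: 3 scales × 4 groups × 2 = 24 values.
- Counts per level instead: FPS-R 6 × 4 = 24, Draize 5 × 4 × 2 = 40, total 64 cells.
- Listing rows, with adolescents dosed twice: 6 + 6 + 2 × 6 = 24 for 6 evaluable per group; 8 + 8 + 2 × 8 = 32 at the protocol's 8 per cohort; 12 + 12 + 2 × 12 = 48 at the SAP's 12 per group.

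**The case against.** The strongest reply is that this is a choice of summary. Protocol and SAP agree on it, no test, dose decision or stopping rule uses the scores, and incidence with onset, duration and type is a coherent description of about 6 children per group. That stands, and it limits the point to a reporting improvement. A reader might infer that the SAP departs from the protocol here. It does not.

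A reader might also infer that the plan reports no intensity anywhere. The documents do not support that. Figure 5 is unseen, and its caption refers to local tolerability in general, so it could plot scores. Reactions needing intervention are graded as adverse events, so the top Draize grade may often be captured by that route; how often is unknown. SAP 2 also promises a descriptive analysis of all endpoints, which does not forbid score-level summaries. But SAP 2.5.4 and the shell footnotes define the analysed variable as above 0, and no shell carries anything finer.

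On the 180-minute column, each shell row has a single N beside the age group and dose. The vital-signs shell, by contrast, prints an N at each time. That layout fits an all-dosed denominator at least as well, and the SAP does not say whether a score skipped by design counts as missing. A reader might infer that the percentage is certain to be overstated; that follows only if the SAP 2 rule is applied literally.

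Finally, FPS-R asks about discomfort remaining at the time of asking, first at about 10 minutes. It does not measure peak pain, and a worst-score summary cannot recover the first minutes.

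**Conclusion.** The point holds as a minor one. In the visible tables and listings, the intensity of injection-site reactions that needed no intervention is not reported, although the scores are in the case report form. The documents give no expected score distribution, so the size of the information loss cannot be stated beyond the number of levels merged.

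The 180-minute denominator is unsettled. Under the literal SAP 2 rule, the percentage in the assumed example exceeds the all-dosed rate by a factor between 1 and 6; under the fixed-N reading there is no inflation. The example rests on assumed counts, and the printed n lets a careful reader see how many children are still reacting.

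**What to change.** Keep the rows for score above 0. Add to each of the three shells, by age group and dose, the median and maximum of each child's worst recorded post-dose score, with FPS-R, erythema and edema kept separate. A by-subject listing of the scores would serve equally. Label the FPS-R figure as discomfort remaining at about 10 minutes or later. Where fewer than half the children react the median will be 0, so the maximum or the listing carries the information.

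For 180 minutes, add one sentence to SAP 2.5.4: the denominator is all dosed children, and those not re-scored under the 30-minute rule count as having no reaction. Footnote the number actually re-scored. This assumes no late onset, and the footnote lets the reader judge that.

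The cost is 24 values, or one listing of 24 to 48 rows, plus one sentence and a footnote. Counts per level would also work, but would add 64 cells, most of them probably 0 or 1. No new data are needed and the primary analysis is unaffected.

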#### 5.3.2. Secondary Endpoint

The secondary endpoints for this study are as follows:

- Pharmacokinetic parameters, including: descriptive analysis of AUC0-120m, Cmax and Tmax of the different age cohorts.
- Pharmacodynamic characteristics, including: plasma glucose AUC0-120m, Cmax, Tmax and time to achieve an increase in plasma glucose of at least 25 mg/dL.
- Safety-related parameters including:
  - Vital signs
  - Incidence of adverse events (AEs) and serious adverse events (SAEs)
  - Subjective injection site discomfort using the Faces Pain Scale [FPS-R]
  - Subjects with sufficient comprehension will further describe the nature and duration of any injection site discomfort using a second questionnaire (Appendix 1).
  - Erythema and/or edema formation at site of injection assessed by an investigator using the modified Draize scale (see Appendix 2)

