**Injection Site Discomfort Description and Duration Questionnaire**

*Study Personnel Instructions:* Question 1a should be completed by the subject at **10±5** minutes following the injection of study drug. Any subject reporting discomfort other than “none,” should complete question 1b. Any subject reporting duration of discomfort of “at least 10 minutes” should complete follow-up question 1c at the end of the study visit. The goal is for the subject to report the qualitative nature and duration of discomfort, if any, associated with injection of study drug, ignoring any transient pain associated with needle insertion.

*Subject Instructions:* Please answer question 1a and, if they apply to you, questions 1b and 1c. In answering these questions, you should ignore any pain from insertion of the needle.

1a. How would you describe any discomfort you felt from the study drug? (Check **all** that apply):

- None (**Please ignore question 1b.**)
- Pain (e.g., throbbing, soreness, muscle ache)
- Itching
- Tingling, twitching or numbness
- Irritation (e.g., burning, stinging)

Other or additional comments: \_\_\_\_\_

1b. About how long did the discomfort last after the injection? (Check one):

- Less than 1 minute
- 1-2 minutes
- 3-5 minutes
- 6-9 minutes
- at least 10 minutes (**Please complete question 1c before leaving the clinic.**)

1c. In total, how long did the discomfort last after the injection? (Please enter a number below):

\_\_\_\_\_ Minutes

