
Figure 5: Local tolerability by age group and by treatment dose for subjects aged 12.0-<18.0

[figure not shown]

Table 19: Time of onset and duration of discomfort and discomfort description by age group and by treatment dose for subjects aged 12.0-<18.0				
	2.0-<6.0 years (N=X^{a,b})	6.0-<12.0 years (N=X^a)	12.0-<18.0 years with 1.0 mg (N=X^a)	12.0-<18.0 years with 0.5 mg (N=X^a)
Time of Onset, minute				
N	x	x	x	x
Mean (SD)	xx.x (xx.x)	xx.x (xx.x)	xx.x (xx.x)	xx.x (xx.x)
Median	xx	xx	xx	xx
[Min-Max]	[xx-xx]	[xx-xx]	[xx-xx]	[xx-xx]
Duration – n (%)				
< 1 minute	x (x.x)	x (x.x)	x (x.x)	x (x.x)
1-2 minutes	x (x.x)	x (x.x)	x (x.x)	x (x.x)
3-5 minutes	x (x.x)	x (x.x)	x (x.x)	x (x.x)
6-9 minutes	x (x.x)	x (x.x)	x (x.x)	x (x.x)
10-15 minutes	x (x.x)	x (x.x)	x (x.x)	x (x.x)
16-30 minutes	x (x.x)	x (x.x)	x (x.x)	x (x.x)
30-120 minutes	x (x.x)	x (x.x)	x (x.x)	x (x.x)
121-180 minutes	x (x.x)	x (x.x)	x (x.x)	x (x.x)
Discomfort Description ^c				
Pain (e.g. throbbing, soreness, muscle ache) – n (%)	x (x.x)	x (x.x)	x (x.x)	x (x.x)
Itching – n (%)	x (x.x)	x (x.x)	x (x.x)	x (x.x)
Tingling, twitching, or numbness – n (%)	x (x.x)	x (x.x)	x (x.x)	x (x.x)
Irritation (e.g. burning, stinging) – n (%)	x (x.x)	x (x.x)	x (x.x)	x (x.x)

^aOnly those who reported having at least one discomfort post-injection are included in the table.

^bX subjects are not applicable because they are too young for comprehension.

^cA subject may report more than one discomfort.

Listing 3: Pregnancies and outcomes

Subject ID	Age group	G-Pen™ dose	Number of Embryos, Fetuses, and/or Infants	Outcome	Congenital Anomaly?	Gestational Age (weeks and days)	Gender	Weight (lbs)	Length (in)	Head Circumference (cm)

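### The injection-site discomfort questionnaire has no onset item and no still-present option, so the planned onset row has no source in the documents and durations may be recorded too short

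*SAP*

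**What the plan says.** Three summaries are planned. Protocol section 13.3.4 states: "Descriptive statistics (only) will be provided for time of onset and duration (of discomfort) and discomfort description". SAP section 2.5.4 repeats the commitment, "Descriptive statistics will be provided for time of onset, duration (of discomfort), and discomfort description", by age group and, for the oldest group, by dose. The mock-up is Table 19 in SAP Appendix I, although the SAP text cites it as Table 18. It has a continuous row headed "Time of Onset, minute", with N, mean, SD, median and range, and duration bands that run up to 121-180 minutes.

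The listed endpoint is narrower. Protocol section 5.3.2 says that subjects with sufficient comprehension will "further describe the nature and duration of any injection site discomfort using a second questionnaire". SAP section 1.2.2 has the same scope. Onset is not mentioned in either.

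The questionnaire in Protocol Appendix 1 has three items:

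- Item 1a begins "1a. How would you describe any discomfort you felt from the study drug" and is answered 10±5 minutes after injection.
- Item 1b is answered by anyone who reports discomfort in 1a. It offers five bands: under 1, 1-2, 3-5, 6-9, and 10 minutes or more.
- Item 1c asks for total minutes. Only subjects in the top band of 1b "should complete follow-up question 1c at the end of the study visit".

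**The concern.** Two of the three planned summaries do not match the form that feeds them. Onset is to be reported in minutes, yet no item asks for it. Duration is to be reported up to three hours, yet the form decides at about 10 minutes, and possibly as early as 5, whether a child will be asked again. It has no way to record that discomfort is continuing.

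The duration error would run in one direction. A long-lasting reaction can be filed as a short one, but the form has no matching mechanism that lengthens a short one. Nature and duration of discomfort is a listed secondary safety endpoint, so the table could make local tolerability look better than it was.

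**Working it through.** The plan states no figure to reproduce here. The check traces each planned summary to the item that would collect it, then sets the assessment window against the answer bands.

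**Tracing the summaries**

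| Planned summary | Source in Appendix 1 | Result |
|---|---|---|
| Description | 1a | collected |
| Duration | 1b, then 1c for the top band | collected, but can be cut short |
| Time of onset | none of the three items | no source in the documents |

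Other possible sources of onset do not fill the gap. The Faces Pain Scale records current pain at fixed times (Appendix 1). Protocol section 12.2 keeps injection site reactions out of adverse event reporting unless they need medical intervention. Items 1b and 1c count time from the injection, so for late-starting discomfort onset and duration would be mixed.

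**Window against bands**

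The window is 10−5 = 5 to 10+5 = 15 minutes. Assume that discomfort starts at injection, is still present at time t, and that 1b is answered together with 1a. The longest duration that can truthfully be reported is then t.

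| Asked at minute | Highest truthful band in 1b | Reaches 1c? |
|---|---|---|
| 5 | 3-5 minutes | no |
| 6, 7, 8, 9 | 6-9 minutes | no |
| 10 to 15 | 10 minutes or more | yes |

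At 5 of the 11 whole-minute times allowed, the follow-up question cannot be reached. On a continuous scale the share of the window is (10−5)/(15−5) = 50%. This describes the permitted window, not the expected share of assessments, which would require an assumption such as uniform timing.

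**Illustration (constructed)**

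A child asked at minute 6, whose discomfort goes on to last 60 minutes, is stored in the 6-9 minute band. The understatement is at least 60−9 = 51 minutes. That child cannot appear in any of the four longer bands of Table 19.

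**Weight of one child**

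The cohort target is 6 evaluable subjects. If all 6 report discomfort, one misfiled child moves a band by 1/6 = 16.7 percentage points. If the SAP's maximum of 12 per age group all report it, the shift is 1/12 = 8.3 points. Table 19 includes only children who report discomfort, so the denominator can be smaller and the shift larger.

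**Bands**

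The bands 16-30 minutes and "30-120 minutes" both contain a value of exactly 30. Item 1c takes a free number, so 30 is a possible answer.

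**The case against.** The strongest counter-argument is Protocol section 10.2.1, step 13a. It has subjects complete the Appendix 1 questionnaires, in the plural, at 10±5 and 30±5 minutes, and again at 180±5 minutes if the 30-minute pain score is above 0. If that covers the description and duration questionnaire, a child with continuing discomfort would be asked 1b again at 25-35 minutes, could choose the top band, and would reach 1c. The 60-minute illustration would then be caught. This objection stands in part. However, Appendix 1 attaches only the 10±5 minute time to this questionnaire and sets 1c at the end of the visit, while its instructions for the pain scale carry the 10, 30 and end-of-visit pattern. The two places conflict, and the SAP does not say which 1b answer would count if there were two.

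Second, Appendix 1 gives 1b no time of its own. That it is answered together with 1a is the natural reading, but it is an inference. At the nominal 10 minutes the top band can be true.

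Third, the pain scale at 30 minutes, and at 180 minutes where it applies, shows pain that persists, and the SAP tabulates it. This stands, but it does not correct the duration rows. It may miss itching or tingling, no SAP rule links the two instruments, and discomfort that ends between minute 10 and the 25-35 minute reading leaves no trace of its length.

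Fourth, the case report form is not among the documents, so an onset field there cannot be excluded.

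A reader might infer more than this supports:

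- **That the questionnaire fails all three planned summaries.** It does not. Description is collected and duration can be tabulated.
- **That a listed endpoint has no data.** Onset is a planned summary, but the listed endpoint covers nature and duration only.
- **That half of all assessments are affected, or that understatements near 51 minutes are typical.** The documents give no distribution of assessment times or of discomfort duration.

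**Conclusion.** The point holds in a limited form. On the documents provided, the onset row in Protocol section 13.3.4, SAP section 2.5.4 and Table 19 has no data source. Under the Appendix 1 instructions, discomfort still present when a child is asked before minute 10 is recorded as finished and short, which gives a possible downward bias in duration.

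The size of that bias is unknown. It rests on three assumptions: 1b is answered when 1a is, some assessments fall in minutes 5 to 9, and the questionnaire is not repeated at 30 minutes. Local tolerability is summarised descriptively only, and the primary endpoint is untouched. This is a minor point, worth correcting because the correction is so cheap. The overlapping bands and the mismatched table number are clerical.

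**What to change.** - Add a still-present option to item 1b and let it trigger 1c at the end of the visit.
- Reconcile Protocol section 10.2.1, step 13a, with Appendix 1 on when this questionnaire is given. If it is repeated, state in the SAP which answer is analysed.
- Either add an onset item, or delete the onset summary from Protocol section 13.3.4, SAP section 2.5.4 and the mock-up. If the case report form already has an onset field, name it in the SAP.
- If data are already collected, flag 1b answers below the top band that were given before minute 10 as possibly censored, and footnote the table. This needs the actual completion time to have been recorded, which the form as reproduced does not show.
- Change the overlapping band to 31-120 minutes and align the table number with the SAP text.

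The cost is one form edit and a few lines of protocol and SAP wording. No extra visit or blood sample is needed. A child who ticks the new option answers one more question before leaving.
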